4.5.4.5 Dose-limiting Toxicity

The period for evaluating DLTs will be from the time of first administration of MEDI-565 through the first 28-day cycle. Subjects who do not receive 1 full cycle of MEDI-565 for reasons other than a DLT will be replaced with another subject in the same dose level. Grading of DLTs will be according to the [NCI CTCAE v4.03](#).

Dose-limiting toxicities include any Grade 3 or greater nonhematological toxicity or laboratory abnormality that cannot be reasonably ascribed to another cause (such as disease progression or accident) with the following exceptions:

- 1) Grade 3 or 4 elevations in liver transaminases (either AST, ALT or both) that resolve to $\leq 2 \times$ ULN or baseline within 14 days after cessation of MEDI-565 infusion

- 2) Grade 3 changes in serum electrolytes in subjects with previously identified electrolyte abnormalities that resolve within 48 hours of initiation of repletion or cessation of MEDI-565
- 3) Grade 3 elevations in temperature that do not result in an SAE and resolve with or without medical therapy, unless associated with other symptoms of cytokine release syndrome
- 4) Grade 3 inflammatory reaction attributed to a local antitumor response (eg, inflammatory reaction at sites of metastatic disease, lymph nodes, etc)
- 5) Grade 3 infusion-related event that resolves with appropriate supportive care within 12 hours, with no associated sequelae

For hematological toxicities, any related Grade 3 or greater hematological toxicities or laboratory abnormalities will be considered to be DLTs with the following exceptions:

- Grade 3 or greater lymphopenia
- Grade 3 neutropenia that resolves prior to the next cycle of MEDI-565

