Once the MTD or OBD is determined, a total of 60 additional subjects (20 each with refractory pancreatic adenocarcinoma, refractory CRC, or refractory gastroesophageal cancer) may be enrolled at MTD or OBD in a dose-expansion phase. Commencement of the dose-expansion phase and the selection of any tumor types will be based on any previously observed signal of antitumor activity and the safety profile of MEDI-565 emerging from the dose-escalation phase. Subjects in the dose-expansion phase will receive MEDI-565 at the MTD or OBD as a 3-hour IV infusion per day for 5 consecutive days every 28 days (defined

as 1 cycle). Subjects in the dose-expansion phase are considered evaluable for antitumor activity if they receive at least 2 full cycles of MEDI-565 or discontinue due to progressive disease or toxicity. Nonevaluable subjects in the dose-expansion phase will be replaced. All subjects who receive any amount of MEDI-565 will be considered evaluable for safety.

A study flow diagram is shown in [Figure 3.1-1](#).

[figure not shown]

Figure 3.1-1 Study Flow Diagram

CRC = colorectal cancer; MTD = maximum tolerated dose; OBD = optimum biologic dose

The endpoints to be measured in this study are described in Section 7.3.

Standard 3+3 design for study enrollment is shown in [Figure 3.1-2](#).

[figure not shown]

Figure 3.1-2 Standard 3+3 Flow Diagram

DLT = dose-limiting toxicity; MTD = maximum tolerated dose; OBD = optimum biologic dose

The diagram above shows the work flow of a standard “3+3” design. A dose-escalation trial enrolls a group of 3 subjects at dose level X. If no subject experiences a DLT, escalate to the next higher dose level, X+1. If 2 or more subjects experience a DLT, stop dose escalation. If 1 subject experiences a DLT, expand dose level X to a total of 6 evaluable subjects. If 1 of 6 experiences DLT, escalate to dose level X+1. If 2 or more of 6 experience DLT, stop dose escalation. If the study stops at dose level X, then the MTD is estimated as the prior dose level (X-1).

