4.5.4.2 Dose Escalation

Rules for dose escalation are as follows:

- 1) The MTD will be determined based on the assessment of a DLT (refer to Section [4.5.4.5](#)) during the DLT period, which is defined as the time from the first dose of MEDI-565 to 28 days after the first dose of MEDI-565 (Cycle 1). Subjects are considered evaluable for assessment of DLT if they receive at least 1 full cycle of MEDI-565 (Days 1-5, Cycle 1) and complete the safety follow-up (Days 6-28, Cycle 1) through the DLT evaluation period or experience any DLT. Nonevaluable subjects will be replaced.
- 2) If a Grade 3 or greater AE or toxicity corresponding to a DLT occurs in any cohort, that cohort will be expanded to 6 evaluable subjects. If 1 of 6 subjects experiences a DLT in the expanded cohort, dose escalation will proceed to the next dose level. If ≥ 2 subjects experience a DLT in a given cohort, the MTD will have been exceeded and the next lower dose will be evaluated as the MTD. The MTD will be defined as the highest dose, up to 10 mg, at which no more than 1 out of 6 subjects experience a DLT.
- 3) If the MTD is exceeded during dose escalation (≥ 2 out of 6 subjects experience a DLT in a given cohort), and the prior lower dose level is demonstrated to be safe (≤ 1 out of 6 subjects with DLTs), an intermediate dose may be evaluated if appropriate based on available PK, pharmacodynamics, safety, and clinical data. Dose escalation must stop prior to reaching the dose and exposure for the cohort that exceeded the MTD.
- 4) If significant antitumor activity is observed during dose escalation prior to identifying an MTD and before reaching the 10 mg dose, the Sponsor may halt dose escalation without determining the MTD. In this case, an OBD below the MTD may be chosen for the dose-expansion phase of the study, provided this is supported by the safety, antitumor activity, PK, pharmacodynamic, and biomarker data.

A study-specific Dose Escalation Committee will provide ongoing safety surveillance of the study, with regularly scheduled reviews of safety and other relevant data. This committee will be responsible for dose-escalation decisions and making recommendations regarding further conduct of the study. The sponsor will notify sites when enrollment into each dose cohort has been completed and when enrollment into the next dose cohort is permitted. In addition, MedImmune's internal safety monitoring committee (ie, SMC or equivalent), provides safety

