6.1.3 Other Events of Special Interest

6.1.3.1 Hepatic Function Abnormality

A 'hepatic function abnormality' of special interest to the sponsor is defined as any increase in ALT or AST to greater than $3 \times \text{ULN}$ **and concurrent** increase in bilirubin to greater than

$2 \times$ ULN. Concurrent findings are those that derive from a single blood draw or from separate blood draws taken within 8 days of each other. In the event of hepatic function abnormality, where the etiology is unknown, follow-up investigations and inquiries should be initiated promptly by the investigational site based on medical judgment to make an informed decision regarding the etiology of the event.

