6.4.3.2 Hepatic Function Abnormality

Hepatic function abnormality (as defined in Section 6.1.3.1) in a study subject, with or without associated clinical manifestations, where the etiology is unknown, is required to be reported as "hepatic function abnormal" *within 24 hours of knowledge of the event* to MedImmune Patient Safety using the Safety Fax Notification Form (see Section 6.4.2.2 for contact information). The investigator shall review the data with the medical monitor. The investigator should use clinical judgement to establish the cause based on local standard of care and follow the subject by conducting testing as clinically indicated. If, after appropriate workup, in the opinion of the investigator, the underlying diagnosis for the abnormality remains unexplained, discontinuation of dosing for this subject should be considered.

Each reported event of hepatic function abnormality will be followed by the investigator and evaluated by the sponsor. If the etiology of the event remains unconfirmed and/or is considered related to investigational product (see Section 6.2.2.1), a prompt cumulative

review of safety data and the circumstances of the event in question will be conducted and assessed by the MedImmune Safety Monitoring Committee (SMC) (see Section 6.5) to determine whether continued dosing of current study subjects and/or study entry should be interrupted, whether the protocol will be modified, or whether the study will be discontinued permanently. Review and approval by the SMC is required for resumption of subject dosing or study entry in the event that the study is interrupted. Where applicable, regulatory authorities and IRBs/IECs will be notified of any actions taken with the study.

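### DLT exception 1 for transaminase rises has no bilirubin condition, so a resolving Grade 3-4 AST/ALT rise with bilirubin above 2 × ULN but below Grade 3 can be scored as no DLT

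*Protocol*

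**What the plan says.** Protocol section 4.5.4.5 makes any nonhematological toxicity or laboratory abnormality of Grade 3 or higher a DLT unless it can reasonably be put down to another cause, and then lists five exceptions. The first covers "Grade 3 or 4 elevations in liver transaminases (either AST, ALT or both) that resolve to" 2 × ULN or less, or baseline, within 14 days of stopping the infusion. Bilirubin is not mentioned, and there is no reference to section 6.1.3.1.

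Section 6.1.3.1 says that a hepatic function abnormality "of special interest to the sponsor is defined as any increase in ALT or AST to greater than" 3 × ULN together with a concurrent bilirubin above 2 × ULN. It also fixes the timing: "Concurrent findings are those that derive from a single blood draw or from separate blood draws taken within 8 days of each other".

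Section 6.4.3.2 requires a prompt cumulative review by the Safety Monitoring Committee (SMC). The trigger reads "If the etiology of the event remains unconfirmed and/or is considered related to investigational product". For the individual subject, if after workup "the underlying diagnosis for the abnormality remains unexplained, discontinuation of dosing for this subject should be considered".

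Escalation runs on DLT counts. Section 3.1 says "If no subject experiences a DLT, escalate to the next higher dose level, X+1". Rule 2 of section 4.5.4.2 says "If 1 of 6 subjects experiences a DLT in the expanded cohort, dose escalation will proceed to the next dose level", and two or more DLTs in a cohort mean that the MTD has been exceeded.

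**The concern.** The exception turns on one thing only, whether the AST/ALT rise resolves in time. It is the only nonhematological exception that reaches Grade 4. Exception 3 shows that the protocol does take an exception back when another sign changes its meaning: the fever exception is lost if other cytokine release symptoms are present. Exception 1 has no such condition, although elsewhere the protocol treats a transaminase rise with raised bilirubin as a different matter from a transaminase rise alone.

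Two things depend on the DLT label. The first is the MTD, a primary objective, which section 4.5.4.2 defines by the number of DLTs in six subjects. The second is withdrawal. Criteria 9 and 10 of section 4.2.3 stop drug for a DLT or, after Cycle 1, for an event meeting DLT criteria (criterion 10 allows case-by-case exceptions agreed with the FDA). An excepted event has no such automatic stop at its first occurrence. From Cycle 2, Table 4.5.4.4-1 allows dosing at 50% to go on if the toxicity resolves to Grade 1 or baseline within 7 days.

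Hepatotoxicity is among the potential risks named in section 1.4.

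**Working it through.** **1. Which events fall in the gap.** Take a Grade 3 or 4 AST/ALT rise that resolves in time and has no other cause.

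- Bilirubin at or below 2 × ULN: the combined definition in 6.1.3.1 is not met and exception 1 applies as intended.
- Bilirubin of Grade 3 or higher: no exception covers it, so it is already a DLT.
- Bilirubin above 2 × ULN but below Grade 3: exception 1 removes the transaminase rise, and the bilirubin value is not a DLT by itself.

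The third case is the gap. Entry requires bilirubin of at most 1.5 × ULN (4.2.1, criterion 8a), so a value above 2 × ULN exceeds the entry limit. The protocol grades by CTCAE v4.03 but prints no bilirubin limits. If Grade 3 started at 2.5, 3 or 5 × ULN, the band would be 2-2.5, 2-3 or 2-5 × ULN. If it started at 2 × ULN or lower, there would be no gap. The link to 6.1.3.1 also assumes that Grade 3 AST/ALT lies above 3 × ULN, which is not printed either.

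**2. How the event is recorded.** Section 6.3.2.1 has an unexplained combined abnormality reported as *hepatic function abnormal*, and one of known cause by its diagnosis. Neither is a transaminase elevation in the sense of exception 1, so at Grade 3 or higher, and not ascribed to another cause, either is a DLT. Section 6.2.1 leaves the grade of events not listed in CTCAE to medical judgment. The same laboratory values can therefore score as a DLT at one site and not at another.

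**3. Rule trace.** This needs no event rate.

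| Cohort | Event not counted | Event counted |
|---|---|---|
| 6 subjects, 1 other DLT | 1/6: escalate | 2/6: MTD exceeded |
| First 3 subjects, no other DLT | 0/3: escalate | 1/3: expand to 6 |

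The second row assumes that only a DLT expands a cohort, as section 3.1 states. Rule 2 of 4.5.4.2 begins "If a Grade 3 or greater AE or toxicity corresponding to a DLT occurs in any cohort", which could also be read as expanding for any Grade 3 event. On that reading the cohort is expanded either way. The first row holds on both readings.

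**4. Reproducing the plan's figure.** For true DLT rate p, the 3+3 rule escalates with probability

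S(p) = (1−p)³ + 3p(1−p)² × (1−p)³.

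S(0.1) = 0.729 + 0.177 = 0.906 and S(0.2) = 0.512 + 0.197 = 0.709, against 0.91 and 0.71 in Table 7.5-1. The other seven entries also reproduce.

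**5. Illustration.** The protocol gives no rate for the combined event. Assume rate q in subjects with no other DLT, and rate p for other DLTs. Not counted: S(p). Counted: S(p+q).

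| p | q | Not counted | Counted | Difference |
|---|---|---|---|---|
| 10% | 1% | 0.906 | 0.889 | 0.017 |
| 10% | 2% | 0.906 | 0.871 | 0.035 |
| 10% | 5% | 0.906 | 0.814 | 0.092 |
| 20% | 1% | 0.709 | 0.687 | 0.022 |
| 20% | 2% | 0.709 | 0.665 | 0.044 |
| 20% | 5% | 0.709 | 0.600 | 0.109 |

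If the event expands the cohort without being counted, the not-counted probability becomes (1−p−q)³ + [(1−p)³ − (1−p−q)³] × [(1−p)³ + 3p(1−p)²] + 3p(1−p)⁵. At p = 20%, q = 5% this is 0.699 in place of 0.709. Over the table the differences become 0.016 to 0.099, so expanding without counting moves the escalation probability by less than 0.01.

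**The case against.** The strongest reply is that a DLT rule and a special-interest reporting rule serve different purposes, so an event may need SMC review without being a DLT. That is right. A reader might infer that sections 4.5.4.5 and 6.4.3.2 contradict each other; they do not. What is missing is a condition in one of them.

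A reader might also infer that escalation would go ahead unchecked, or that the subject would simply stay on drug. The text does not support that:

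- The Dose Escalation Committee reviews all adverse events and laboratory data before deciding (6.5), and toxicities that are not DLTs may prompt an intermediate dose (4.5.4.2).
- The SMC review determines whether dosing or entry should be interrupted (6.4.3.2), and the SMC may suspend either (6.5).
- Criteria 2 and 15 of section 4.2.3 allow the subject to be stopped.
- Table 4.5.4.4-1 stops drug at a second Grade 3 or 4 occurrence after Cycle 1.

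For the same reason, a rule that escalation must wait for the SMC would be a process preference and is not part of this point. None of these safeguards changes the DLT count.

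It can further be said that recording under 6.3.2.1 already closes much of the gap, and that a site scoring only the transaminases departs from that section. This stands in part. What remains is a combined event graded below 3, which the protocol permits.

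Finally, the visible text reports no liver signal with MEDI-565: the Cohort 10 DLTs were hypoxia, and section 1.4 says that liver enzyme rises with EpCAM-directed agents need not predict toxicity here. That limits how often the gap would matter.

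**Conclusion.** The point holds as a narrow gap in a definition and merits a low-priority change. Its existence, not only its width, rests on CTCAE Grade 3 bilirubin starting above 2 × ULN. It also needs timely resolution, no other cause, and a combined event not graded 3 or higher. A reader might infer that any combined liver abnormality escapes the DLT count; that goes too far for the reasons in steps 1 and 2 of the working.

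Within those conditions the firm result is the rule trace: one event decides whether a cohort stands at 1/6 or 2/6. The probabilities show scale only. They rest on assumed rates of 1% to 5% and on a 3+3 applied mechanically, without committee judgment, and should not be read as expected effects. Table 7.5-1 is correct as printed.

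**What to change.** In exception 1 of section 4.5.4.5, insert after the bracketed AST/ALT wording, and before the resolution condition: *, without concurrent bilirubin > 2 × ULN (as defined in Section 6.1.3.1),*. The 14-day resolution condition stays as it is. The threshold and the meaning of concurrent are the protocol's own, and the lead-in still excludes events with another cause.

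No new tests are needed, because section 5.3.3 already has AST, ALT, ALP and total bilirubin tested and assessed together. The cost is an occasional cohort expansion, or a subject who must stop drug under criterion 9 or 10 of section 4.2.3.

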Two of 5 subjects in Cohort 10 (3 mg) experienced hypoxia within several hours after completion of the Cycle 1, Day 1 infusion that met the protocol definition of DLT. Under previous versions of the protocol, the occurrence of dose-limiting hypoxia in two subjects in Cohort 10 (3 mg dose) would have indicated that the MTD has been exceeded at the 3 mg dose. However, available data suggest that the observed DLTs were reversible and potential future cases of hypoxia temporally associated with MEDI-565 administration should be manageable with the implementation of additional risk mitigation measures including prophylactic dexamethasone administration prior to MEDI-565 administration and additional blood pressure, heart rate, and pulse oximetry monitoring during and following administration of MEDI-565. Thus, under Amendment 4 of the protocol, dosing will re-start at the next previously lower dose of 1.5 mg (Cohort 11) with implementation of the additional risk mitigation measures outlined above for all new subjects. Provided no more than 1 out of 6 subjects experience DLTs in the preceding cohort, dose escalation will continue in sequential fashion and re-evaluate the 3-mg dose (Cohort 12), followed by 5 mg (Cohort 13), 7.5 mg (Cohort 14), and 10 mg (Cohort 15) doses.

Currently, there are no anticancer agents approved by the United States Food and Drug Administration (FDA) with a CD3 effector mechanism to comparatively assess the potential safety and tolerability of MEDI-565, although one such agent is approved in the EU. A monoclonal antibody directed against CD3, muromonab-CD3 (Orthoclone OKT3) is approved by the FDA for use in acute transplant rejection. The most frequent adverse events (AEs) associated with muromonab-CD3 use are symptoms related to cytokine release syndrome, associated most strongly with the first few doses, which range from self-limited flu-like symptoms to more severe shock-like reactions. Cardiorespiratory findings included dyspnea, chest pain, bronchospasm, tachypnea, cardiovascular collapse, hypotension and adult respiratory distress syndrome (ARDS). Central nervous system events include seizures, encephalopathy, cerebral edema and aseptic meningitis, some resulting in permanent impairment. Other serious and occasionally fatal hypersensitivity reactions include cardiovascular collapse, hypotension, shock, tachycardia, angioedema, bronchospasm, urticaria and pruritus ([Orthoclone OKT3 package insert, 2004](#)).

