administration prior to MEDI-565 administration and additional blood pressure, heart rate, and pulse oximetry monitoring during and following administration of MEDI-565. To minimize risk to subjects, Amendment 4 of Study MI-CP216 will re-start dosing at the next previously lower dose of 1.5 mg (ie, 1 dose level below the level at which the hypoxia events were observed) with implementation of the additional risk mitigation measures outlined above for all new subjects. A dose of 1.5 mg was chosen to re-start the study because it was judged to be more conservative from a safety standpoint and consistent with standard practice to de-escalate one dose level below the dose level (ie, 3 mg) at which the DLTs of hypoxia were observed. Provided no more than 1 out of 6 subjects experience DLTs in the preceding cohort, dose escalation is planned to continue in sequential fashion and re-evaluate the 3 mg dose (Cohort 12) followed by 5 mg (Cohort 13), 7.5 mg (Cohort 14), and 10 mg (Cohort 15) doses.

MEDI-565 will be administered by IV infusion over 3 hours per day for 5 consecutive days (ie, Days 1 through 5) every 28 days (defined as 1 cycle). Subjects in the dose-escalation phase are considered evaluable if they receive at least 1 full cycle of MEDI-565 and complete the safety follow-up through the DLT evaluation period of 28 days after the first dose of MEDI-565, or experience any DLT as defined in Section 4.5.4.5. Subsequent cycles may be delayed for up to 7 days for management of some types of toxicity (Section 4.5.4.4) or to accommodate scheduling issues. Nonevaluable subjects, defined as any subject discontinued during the DLT evaluation period for reasons other than a DLT, will be replaced in the same dose cohort. No intra-subject dose escalation will be allowed.

Dose escalation will continue until the MTD or a maximum dose of 10 mg is reached. In the event that no DLTs are observed during dose escalation and significant antitumor activity is observed, the Sponsor may halt dose escalation prior to determining the MTD provided that PK, pharmacology, safety and preliminary antitumor activity data support the use of an OBD below the MTD. On determination of the MTD or OBD, additional subjects will be enrolled so that a total of 6 subjects receive the MTD/OBD during the dose-escalation phase.

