Cohorts 1 through 4 were successfully enrolled as single-subject cohorts to minimize the number of subjects with advanced, incurable cancers who are exposed to what are likely to be ineffective doses. Following the observation of a Grade 2 treatment-related AE that occurred in the first subject enrolled into Cohort 5, this cohort was expanded to 3 subjects to further evaluate the safety of the 60 µg dose level. A second subject in Cohort 5 experienced a Grade 2 treatment-related AE. Under the rules of the previous versions of the protocol, dose escalation was to then follow a modified Fibonacci sequence. However, given that no ≥ Grade 3 toxicities or DLTs were observed, dose-escalation continued at approximately

150% increases from 120 µg (starting with Cohort 6) up to 1.5 mg, followed by a 100% dose increase to 3 mg (Cohort 10).

Two of 5 subjects in Cohort 10 experienced DLTs of hypoxia. The hypoxia events could be indicative of pharmacodynamic changes induced by MEDI-565 exposure. Cytokine release may have been a contributing factor, and would be consistent with the mechanism of action and the overall clinical presentation. Under the previous version of the protocol, these 2 DLTs would have indicated that the MTD has been exceeded at the 3 mg dose. Available data suggest, however, that the observed DLTs were reversible and potential cases of hypoxia temporally associated with MEDI-565 administration should be manageable with implementation of additional risk mitigation measures including prophylactic dexamethasone administration prior to MEDI-565 administration and additional blood pressure, heart rate, and pulse oximetry monitoring during and following administration of MEDI-565. Under Amendment 4, it is proposed that dosing can resume at the next previously lower dose of 1.5 mg (Cohort 11) with implementation of specific risk mitigation measures, and provided no more than 1 out of 6 subjects experience DLTs in a given cohort, dose escalation may continue in sequential fashion and re-evaluate higher doses including the 3 mg dose without undue risk, based on the following points:

- The observed hypoxia events occurred within hours after completion of the first MEDI-565 infusion and resolved without sequelae.
- In one case, the hypoxia was successfully managed with corticosteroids which appear to have shortened the time to resolution.

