4.5.4.1 Monitoring of Dose Administration

Subjects will be monitored with assessment of vital signs and pulse oximetry at the following time points: within 15 minutes prior to the start of infusion, every 0.5 hours (\pm 5 minutes) during infusion, immediately post end of infusion (EOI) (\pm 5 minutes), and 0.5 hours (\pm 5 minutes), 1 hour (\pm 5 minutes), and 2 hours (\pm 15 minutes) after the EOI.

Specifically on Cycle 1, Day 1, monitoring of vital signs and pulse oximetry will continue beyond the 2 hour post EOI time point until the start of infusion on Cycle 1, Day 2 as follows:

- 4 hours (\pm 15 minutes), 6 hours (\pm 15 minutes), and 8 hours (\pm 15 minutes) post EOI
- 12 hours (\pm 15 minutes), 16 hours (\pm 15 minutes), 20 hours (\pm 15 minutes), and 24 hours (\pm 15 minutes) post EOI

As with any antibody, allergic reactions to dose administration are possible. Therefore, appropriate drugs and medical equipment to treat acute anaphylactic reactions must be immediately available, and study personnel must be trained to recognize and treat anaphylaxis.

With MEDI-565, the most frequent acute signs/symptoms observed with study drug infusions and assessed as drug-related included: fever, shaking chills, nausea, vomiting, abdominal pain, headache and hypoxia. In the event that such adverse events are noted and are clinically significant, in the absence of a clear alternative etiology, consider steroid treatment (8 mg dexamethasone every 8 hours, or equivalent) until evidence of resolution. If a subject experiences any symptoms such as those listed above, further dosing should be delayed until the subject is clinically stable and the symptoms are resolved. If steroids are clinically indicated to manage any Grade 3 or higher infusion-related signs/symptoms, all remaining doses in the current cycle should be aborted. If steroids are clinically indicated to manage any Grade 2 or lower infusion-related signs/symptoms, the infusion rate should be decreased for the current dose and all remaining doses in the cycle.

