7.3 Endpoints

7.3.1 Primary Endpoints

The primary endpoints are as follows:

- The number (percentage) of subjects with a DLT will be summarized by dose level and overall. The MTD evaluation will be based on the evaluable population for DLT.
- The OBD will be determined based upon analysis of all available subject data including safety, PK, pharmacodynamic, biomarker, and antitumor activity data.
- The number (percentage) of subjects with AEs and SAEs reported through 30 days after the last dose of MEDI-565 will be summarized for all subjects who received at least one dose of study drug (Safety Population). Adverse events and SAEs will be graded according to the [NCI CTCAE v4.03](#) and described by system organ class using the Medical Dictionary for Regulatory Activities (MedDRA) preferred term, severity, and relationship to MEDI-565. Frequency rates will be calculated for each system organ class and MedDRA preferred term.
- The number (percentage) of subjects with significant or important clinical findings in ECG will be summarized by dose cohort.
- The number (percentage) of subjects who had clinically significant laboratory changes recorded as AEs will be summarized. Laboratory hematology and chemistry values will be summarized with the worst value during the study by dose cohort. Clinically significant coagulation profile and urinalysis results will be described.

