- 18) Section 4.5.4.4 (Dose Modification for Toxicity Management): A statement was added to indicate that subjects receiving dexamethasone prophylaxis who have MEDI-565 infusion interrupted for 4 hours or more must restart dexamethasone upon resuming infusion to ensure that sufficient prophylaxis is provided. Text surrounding neurological AEs that must resolve to baseline within 48 hours or they will be considered DLTs was deleted from Table 4.5.4.4-1. No important neurological events have been observed to date; neurological events of Grade 3 or higher will be treated as other AEs in evaluating DLTs.
- 19) Section 4.5.4.5 (Dose-limiting Toxicity): The exception of Grade 3 or 4 elevations in liver transaminases that resolve to $\leq 2 \times$ ULN or baseline within 14 days after cessation of MEDI-565 infusion was modified to delete the allowance for cessation of elevated liver transaminases that resolve to $\leq 2 \times$ ULN or baseline by the next cycle. Grade 3 hypoxia that resolves in less than 12 hours with maximal supportive care was added as an exception to the DLT criteria because these events have been manageable and of short duration. The list of neurological events that will be considered DLTs was deleted. The exceptions to hematological toxicities that are considered to be DLTs was clarified to indicate that these exceptions are in cases considered to be related to MEDI-565.
- 20) Section 5.2 (Schedule of Study Procedures): Table 5.2-1 was modified to add dexamethasone prophylaxis on Cycle 1, Day 1; toxicity monitoring on Days 1 through 5 of each cycle; pulse oximetry monitoring at each visit; additional timepoints for weight measurement; and tumor biopsy during screening and Cycle 1, Day 4.
- 21) Section 5.2.1 (Screening): A statement was added to indicate that screening evaluations that have been obtained for other purposes before a subject provides informed consent may be used if suitable for screening purposes, if the subject consents to their use. Fresh biopsy collection and pulse oximetry were added.
- 22) Section 5.2.2.1 (Cycle 1, Day 1: First Infusion): Dexamethasone prophylaxis was added; additional timepoints for vital signs and pulse oximetry monitoring were added; and additional monitoring for toxicity was added.

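### Section 7.3.1 summarizes DLTs by dose level, which puts 1.5 mg and 3 mg cohorts counted under different DLT definitions on one line

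*Protocol*

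**What the plan says.** **The event that stopped escalation.** Section 1.4: "Two of 5 subjects in Cohort 10 (3 mg) experienced hypoxia within several hours after completion of the Cycle 1, Day 1 infusion". These events met the DLT definition then in force. Section 3.4 adds: "The observed hypoxia events occurred within hours after completion of the first MEDI-565 infusion and resolved without sequelae".

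**The re-test.** Amendment 4 restarts at 1.5 mg (Cohort 11) and returns to 3 mg (Cohort 12), with prophylactic dexamethasone and closer monitoring. Section 3.1 gives the condition: "Provided no more than 1 out of 6 subjects experience DLTs in the preceding cohort, dose escalation is planned to continue in sequential fashion".

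**The DLT definition.** Exception 5 in Section 4.5.4.5 removes a "Grade 3 infusion-related event that resolves with appropriate supportive care within 12 hours, with no associated sequelae". Section 4.5.4.1 lists the acute infusion signs seen so far as "fever, shaking chills, nausea, vomiting, abdominal pain, headache and hypoxia", so hypoxia can fall under that exception. Section 15 (Amendment 4, item 19) dates the change: "Grade 3 hypoxia that resolves in less than 12 hours with maximal supportive care was added as an exception to the DLT criteria", and gives the reason: "because these events have been manageable and of short duration". I use the log only for the date. Exception 5 is the only current exception with a 12-hour limit, so I read it as the present form of that change. The difference in wording is not treated as an error.

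**The summary.** Section 7.3.1: "The number (percentage) of subjects with a DLT will be summarized by dose level and overall". The ECG and laboratory items in the same list are summarized by dose cohort instead.

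**The concern.** Table 4.5.2-1 gives 1.5 mg to Cohorts 9 and 11, and 3 mg to Cohorts 10 and 12. A summary by dose level, read literally, merges each pair. Within each pair the first cohort was counted before the 12-hour exception and the second after it, so a merged line has no single definition.

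The escalation rule works cohort by cohort, so merging does not affect it. It is still affected in another way: the count in Cohort 12 can be lower than in Cohort 10 because less hypoxia occurred, or because the same hypoxia is no longer counted. The sections that justify the re-test (the Abstract, 1.4, 3.1 and 3.4) point to prophylaxis and monitoring and do not mention the change in counting.

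At stake are how the DLT result at 3 mg is read and the basis for the MTD that may be given to up to 60 expansion subjects.

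**Working it through.** **1. Reproduce the plan's figure.** Under the 3+3 rule (0 of 3, or 1 of 3 and then none in the next 3), with counted DLT rate q:

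P(escalate) = (1−q)³ + 3q(1−q)² × (1−q)³

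For q = 10% to 90% in steps of 10 points this gives 0.906, 0.709, 0.494, 0.309, 0.172, 0.082, 0.032, 0.0088 and 0.001. All nine values of Table 7.5-1 are reproduced.

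**2. Inputs for the illustration.**
- Hypoxia rate h at 3 mg: 2/5 = 40% (exact 95% CI 5% to 85%), from Section 1.4, held unchanged. 20% and 60% are shown as alternatives.
- Share e of these events that meets exception 5: not given in the protocol as shown. Assumed, from 0 to 100%.
- No other DLTs: assumed.

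**3. Does a subject with an exempt event stay in the denominator?** The sections do not agree.
- Section 4.5.4.1: if steroids are needed for a Grade 3 or higher infusion-related sign, the remaining doses of the cycle are aborted.
- Section 4.5.4.5: a subject without a full cycle for reasons other than a DLT is replaced. Sections 3.1 and 4.2.4 likewise replace subjects discontinued in the DLT period for reasons other than a DLT.
- Abstract, Sample Size: nonevaluable means discontinued for reasons other than study drug-related toxicity. On that wording a subject stopped by a drug-related exempt event would not be replaced.

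Both cases are therefore computed. Kept evaluable: q = h(1−e). Replaced: q = h(1−e)/(1−he), because only subjects without an exempt event remain.

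For h = 40% and e = 50%:
- Kept: q = 0.4 × 0.5 = 0.20, so P = 0.512 + 3 × 0.2 × 0.64 × 0.512 = 0.709.
- Replaced: q = 0.20/(1 − 0.20) = 0.25, so P = 0.422 + 3 × 0.25 × 0.5625 × 0.422 = 0.600.

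**4. Probability that 3 mg clears with the hypoxia rate unchanged (kept / replaced).**

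| Exempt share | h = 20% | h = 40% | h = 60% |
|---|---|---|---|
| 0% | 0.71 | 0.31 | 0.08 |
| 25% | 0.81 / 0.80 | 0.49 / 0.43 | 0.23 / 0.14 |
| 50% | 0.91 / 0.89 | 0.71 / 0.60 | 0.49 / 0.27 |
| 75% | 0.97 / 0.96 | 0.91 / 0.83 | 0.81 / 0.55 |
| 100% | 1.00 | 1.00 | 1.00 |

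**5. The merged line.** If Cohort 12 ended with 1 DLT in 6, the 3 mg line would read (2 + 1)/(5 + 6) = 3/11 = 27%. The Abstract defines the MTD as the highest dose with DLT frequency below 33%. The merged figure passes that threshold, although 2/5 = 40% does not and the two parts were counted differently.

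**The case against.** The strongest reply is that an exempted event does not disappear. Section 7.3.1 also has all AEs and SAEs summarized by preferred term, severity and relationship, as a primary endpoint. Section 6.5 has the Dose Escalation Committee review all AEs after each cohort. Section 4.5.4.2 allows an intermediate dose after several similar toxicities that are not DLTs. All of this stands. A reader might infer that the primary endpoints cannot reveal persisting hypoxia, and the protocol does not support that. These safeguards are partial, however. They do not enter the DLT count, and none requires a Cycle 1 comparison across cohorts under one definition.

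A reader might also infer that the two Cohort 10 events would have been exempt. This is not shown. Their durations and exact grades are not in the text at hand, nor is the earlier definition in full. Grade 4 events, events beyond 12 hours and events with sequelae still count.

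Nor does the protocol plan to claim that prophylaxis lowers the hypoxia rate. It says that such events should be manageable, and a 12-hour exception is consistent with that.

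Finally, the SAP may separate the cohorts. It might, but the protocol itself fixes the summary by dose level, and escalation decisions are taken during the study.

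**Conclusion.** The point holds as one of comparability and reporting. As written, the DLT summary mixes two definitions at 1.5 mg and at 3 mg, and a lower count in Cohort 12 than in Cohort 10 would not by itself show less hypoxia.

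At an unchanged 40% rate, the chance of clearing 3 mg rises from 31% with no exemption to 60% (exempt subjects replaced) or 71% (kept) with half exempt, and to 100% with all exempt. The 31% belongs to the 3+3 rule itself; only the rise above it comes from the exception. The size rests on an assumed exempt share, a base rate from five subjects, and no other DLTs. It shows what can happen and is not a forecast. It gives no ground for calling the exception clinically wrong.

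**What to change.** **Section 7.3.1**
- Summarize DLTs by cohort. Keep Cohorts 1-10 and 11-15 separate, and do not pool 9 with 11 or 10 with 12.
- Show the counts under a common definition: Cohort 10 re-classified under the current Section 4.5.4.5, and Cohorts 11-15 also under the earlier definition.
- Tabulate by cohort every Cycle 1 Grade 3 or greater infusion-related event, with hypoxia separate, with exact confidence intervals. Include exempted events and subjects replaced after one.

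**Section 6.5**
- Give the Dose Escalation Committee that table beside the DLT count at each escalation decision.

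**Reconcile** exception 5, the aborted-dosing text in Section 4.5.4.1, and the replacement rules in the Abstract and Sections 3.1, 4.2.4 and 4.5.4.5, so that it is clear whether a subject with an exempt event stays in the denominator.

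No change to the clinical DLT definition is proposed. The cost is some wording and one table from AE data already collected, with no added subjects or procedures. The downside is that a cohort cleared on DLTs may look less favourable in the second table.
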